8.1 Grade 4 Toxicities

Participants with life threatening or Grade 4 adverse events thought to be possibly, probably, or definitely related to study treatment will discontinue study treatment and remain on study follow-up and undergo additional visits and therapy as needed for toxicity management. Grade 4 neutropenia determinations will be repeated with duplicate samples to document that neutropenia is present.

8.2 Toxicity Management

Specific expected toxicities lower than grade 4 will be managed as follows:

Adverse Event Action

Neutropenia	Participants who experience Grade 3 neutropenia will receive filgrastim at 300 µg subcutaneously up to 3 times a week. Absolute neutrophil counts will be monitored until return to subject's baseline or <Grade 1. Patient will be asked to return in 1-3 days for evaluation. If grade 3 neutropenia has resolved, patient will return 2-3 days later for repeat evaluation. If grade 3 neutropenia has not resolved at the day 1-3 visit, additional G-CSF will be administered
-------------	--

and the patient will return daily for evaluation and additional G-CSF as medically indicated until resolved. Filgrastim will be discontinued at this time. Interferon will be continued for Grade 3 neutropenia.

CD4 cell count	If the CD4 count declines to <14%, pneumocystis prophylaxis will be offered until the percentage of CD4 cells increases to ≥14%.
Depression	If a BDS score of 14-19 is reported, assessment by the site investigator will be scheduled before the next dose of study drug. If a BDS score of 20-28 is reported, a psychiatric evaluation is required before the next dose of study drug. If a BDS score is >29 or suicidal ideation is reported, participants will permanently discontinue study drug and undergo prompt psychiatric evaluation.

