4.2 Exclusion Criteria

A volunteer will be ineligible to participate in this study if any of the following criteria are met:

1. History of neoplastic disease requiring cytotoxic therapy including hydroxyurea.
2. Use of long-term systemic corticosteroids, immunosuppressive agents, or cytotoxic agents within 60 days prior to enrollment.
3. Any vaccination within 30 days prior to enrollment. Individuals interested in participating who require vaccination will delay screening until 30-day period is completed.
4. Concurrent therapy with investigational cytokines including IL-2 or IL-12 during the course of the study. Prior administration of cytokines is not an exclusion criterion; at least 4 months from most recent cycle of IL-2 or IL-12 is required.
5. Any febrile illness (>38°C) in the 3 weeks prior to enrollment or any acute therapy for a serious infection completed within 30 days prior to enrollment.
6. Current pregnancy or lactation, history of pregnancy in the last 4 months.
7. Preexisting autoimmune disorders including inflammatory bowel diseases, psoriasis, idiopathic thrombocytopenic purpura, lupus erythematosus, autoimmune hemolytic anemia, scleroderma, severe psoriasis, rheumatoid arthritis, and optic neuritis.
8. History of severe retinopathy or evidence of severe retinopathy judged by pre-entry ophthalmologic examination.
9. Known allergy/sensitivity to study drug or its formulation.
10. History of seizure disorders or current anticonvulsant use.
11. Any history of medical conditions associated with chronic liver disease (genetic hemochromatosis, alcoholic liver disease, toxin exposures, and autoimmune hepatitis) or documented cirrhosis due to any cause.
12. History of pulmonary disease associated with functional limitation.
13. Documented history of thyroid disease.
14. Active drug or alcohol use or dependence, which in the opinion of the investigator, would interfere with complying with the study requirements.
15. Known hypersensitivity to *Escherichia coli*-derived products such as filgrastim.
16. Any systemic illness that will make it unlikely that the subject will be able to return for the required study visits.
17. History of, or any condition that in the opinion of the investigator would interfere with the conduct of the study, or it would not be in the best interest of the subject to enroll in this study.

5 Schedule of Visits and Procedures

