7.3 Dose Modifications/Toxicities

A complete blood count with differential (done STAT) will be reviewed before PEG-INF administration at visits 0, 1, 2, and 3. Participants experiencing an adverse event Grade ≤2 may continue at their current dose. No interferon dose modifications will be made in the study but additional visits or monitoring will be permitted to evaluate participants. Toxicity will be evaluated using the Division of AIDS Table for Grading Adults Adverse Events: (<http://rcc.tech-res.com/safetyandpharmacovigilance/>).

8 Management of Toxicities to Study Drug

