8.3 Criteria for Study Permanent Drug Discontinuation

In addition to the criteria for stopping the study drug, the following will constitute criteria for discontinuation of study drug:

1. Development of life-threatening infection or malignancy.
2. Grade 3 or higher neutropenia.
3. Development of clinical depression (see Section 8.5).
4. Acquisition of hepatitis A, B, or C.
5. Pregnancy.
6. If subject's CD4 cell percent remains <14% (see Section 8.2).
7. If it is felt by the site's principal investigator that further participation in the study is no longer in the best interest of the subject.
8. Development of a medical condition, that in the opinion of the investigator, it is in the subject's best interest to discontinue study treatment even if criteria requiring drug discontinuation have not been met.
9. In addition, participants may be withdrawn from the study for:
 - a. Withdrawal of consent
 - b. Non-compliance with study visits or study treatment; subject misses a dose of study drug for reasons other than toxicity
 - c. Termination by sponsor

9 Laboratory Studies

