9.1 Serum Chemistry and Hematology Profiles

Routine safety laboratory tests (Appendix 1) will be performed to monitor clinical status and detect potential drug-related toxicities. Safety tests will be performed at each site's laboratory. During the intensification phase of the study, results of safety tests will be reviewed by the site investigator at each visit before PEG-Interferon administration.

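### Sections 8.2 and 8.3 give opposite interferon instructions for Grade 3 neutropenia, and no text says which one prevails

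*Combined protocol and SAP*

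**What the plan says.** Section 8.2 covers expected toxicities below Grade 4. For Grade 3 neutropenia it gives filgrastim 300 µg up to three times a week with early rechecks. If the count has not recovered at the first recheck, more G-CSF and daily visits follow until it has. The entry closes with "Interferon will be continued for Grade 3 neutropenia", and no condition is attached.

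Section 8.3 is headed as the criteria for permanent drug discontinuation. It opens "In addition to the criteria for stopping the study drug, the following will constitute criteria for discontinuation of study drug", and item 2 reads "Grade 3 or higher neutropenia".

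Four other places bear on the question:

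- Section 7.3 requires a STAT blood count before each dose, rules out dose modification, and says "Participants experiencing an adverse event Grade ≤2 may continue at their current dose".
- Section 8.1 stops treatment for Grade 4 events at least possibly related to it, and adds "Grade 4 neutropenia determinations will be repeated with duplicate samples to document that neutropenia is present".
- Section 9.1 says that during intensification "results of safety tests will be reviewed by the site investigator at each visit before PEG-Interferon administration".
- Item 9b of Section 8.3 allows withdrawal when a "subject misses a dose of study drug for reasons other than toxicity".

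**The concern.** Section 8.2 treats neutropenia as an expected toxicity, and the count is checked before every dose. An investigator holding a Grade 3 result must decide that day whether to inject. One section says to continue and the next says to stop for good. There is no written middle course: doses cannot be reduced, and no text says when a dose is held for neutropenia.

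Patient safety is at stake, in a study whose Section 14 says it offers participants no benefit. Continuing wrongly means more interferon plus filgrastim, whose rare serious risks are set out in Section 12.1.2. Stopping wrongly loses planned doses. Two sites could also act differently on the same count. Section 15.1.1 defines a deviation as any departure from the approved procedures, so whichever rule a site follows, it departs from the other.

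**Working it through.** The plan states no figure on this point, so the check is a comparison of texts followed by simple dose arithmetic.

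**Step 1. The instructions by grade of neutropenia.**

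| Grade | Text that continues interferon | Text that stops it | Result |
|---|---|---|---|
| 2 or lower | 7.3 | none specific to neutropenia | consistent |
| 3 | 8.2 | 8.3 item 2 | contradictory |
| 4 | none | 8.1 (if at least possibly related) and 8.3 item 2 | consistent for related events |

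The conflict is confined to Grade 3.

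**Step 2. Is there a ranking rule?**

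- The lead-in to Section 8.3 adds its list to other stopping criteria. It says nothing about the continuation sentence in Section 8.2, so it ranks the two neither way.
- Item 6 of Section 8.3, on CD4 percentage, is worded as a persistent finding and refers back to Section 8.2. Item 2 has neither feature.
- Section 7.3 permits continuation up to Grade 2 and is silent on Grade 3. That leans toward stopping.
- The duplicate samples for Grade 4 in Section 8.1 would add little if one Grade 3 result had already ended dosing. That leans toward continuing, although duplicates also serve to document the toxicity.
- Section 9.1 requires review before dosing but gives no criterion.
- Item 9b implies that a dose missed for toxicity is not in itself a reason for withdrawal. It does not say when to miss one for neutropenia.

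No ranking rule was found in these sections or elsewhere in the document.

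**Step 3. What the choice means for one participant.** Inputs: 1.5 µg/kg per dose (Section 7.1), given on Days 0, 7, 14 and 21 (Sections 5.4 and 5.5). The full course is 4 × 1.5 = 6.0 µg/kg. If *k* doses were given before the Grade 3 count, item 2 of Section 8.3 yields *k* × 1.5. Section 8.2 yields 6.0, provided no other stopping rule applies.

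| Grade 3 found before the dose on | Total under 8.3 item 2 (µg/kg) | Shortfall from 6.0 (µg/kg) |
|---|---|---|
| Day 7 | 1 × 1.5 = 1.5 | 4.5 (75%) |
| Day 14 | 2 × 1.5 = 3.0 | 3.0 (50%) |
| Day 21 | 3 × 1.5 = 4.5 | 1.5 (25%) |

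If it is first found on Day 28 or later, all four doses have been given and the two rules do not differ in dose.

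**The case against.** The best defence is that Section 8.2 is the detailed procedure and so the intended rule. It sets out filgrastim dosing and rechecks, Section 8.1 reserves confirmation for Grade 4, and Section 4.2 item 15 excludes known hypersensitivity to *E. coli*-"derived products such as filgrastim". A reader might infer that item 2 of Section 8.3 is a slip. The documents do not establish that. The exclusion shows only that filgrastim use was foreseen, and filgrastim rescue fits equally well with stopping interferon. Section 7.3 leans the other way. Nor can item 2 be set aside as a general clause, since it names the same toxicity and grade.

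The opposite inference, that the lead-in makes Section 8.3 override Section 8.2, also fails, because that sentence only adds stopping criteria to other stopping criteria.

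A second defence is that the harm is contained. Counts are reviewed before each dose, G-CSF and extra visits are provided, related Grade 4 events stop treatment, and items 7 and 8 of Section 8.3 let the investigator stop for any participant. Section 16 adds safety review at least yearly. All of this stands and limits the risk. None of it tells the investigator which rule to apply, and the discretion in items 7 and 8 runs one way: it permits stopping and does not lift item 2.

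**Conclusion.** The point holds as an internal inconsistency in a patient-safety rule, and it must be fixed. At Grade 3 neutropenia the protocol directs both continuation and permanent discontinuation, with nothing to choose between them. The conclusion rests on the wording alone and needs no statistical assumption.

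Its size is a difference of one to three doses for a participant whose Grade 3 count is found before the Day 21, 14 or 7 dose. The three-dose figure assumes that no other stopping rule intervenes.

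Two stronger readings are not supported. A reader might take the three post-first-dose checks in 10 participants (3 × 10 = 30 of 4 × 10 = 40 planned doses) as a measure of how often the conflict will arise. That is a count of decision points. The documents give no Grade 3 rate, and because dropouts are replaced, more than 10 people may be dosed. A reader might also infer that the Week 4 primary comparison is compromised. Without a rate the documents do not allow that to be shown, and Section 3.2.2 provides for follow-up through Week 48.

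**What to change.** Keep one rule, by either route:

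- **(a) Continue at Grade 3.** Change item 2 of Section 8.3 to *confirmed Grade 4 neutropenia*, and state in Section 7.3 that Grade 3 neutropenia is managed under Section 8.2.
- **(b) Stop at Grade 3.** Keep item 2 of Section 8.3 and delete the continuation sentence from Section 8.2. The filgrastim procedure can stay as supportive care.

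If the sponsor wants to stop only for Grade 3 neutropenia that does not resolve on G-CSF, changing item 2 alone will not do, because Section 8.2 continues interferon unconditionally while G-CSF is repeated. Define non-resolution in days or G-CSF doses, and make the continuation sentence in Section 8.2 conditional on resolution.

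A separate and minor item can go into the same amendment. The Beck Depression Inventory bands in Section 8.2 are 14–19, 20–28 and above 29, so a score of exactly 29 has no assigned action. Stopping at 29 or above would close the gap, as would extending the middle band to 29. This carries no weight in the verdict.

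The cost is a short protocol amendment, with no extra patients, visits or procedures.

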4.1 Inclusion Criteria

To be eligible for study participation, a volunteer must satisfy all of the following inclusion criteria:

1. Age ≥ 18 years.
2. Documentation of HIV-1 infection by any licensed ELISA test and confirmed by a Western Blot.
3. Receiving a DHHS-approved ARV regimen,.
4. Level of cell-associated HIV RNA ≥ 5 copies/million peripheral blood mononuclear cells (PBMC) done at screening visit 1
5. HIV-1 RNA levels less than detectable by current commercial means (e.g., Roche Amplicor, b-DNA test) for a minimum of 12 months prior to screening at all time points, and with at least 2 measurements in this 12 month window.

6. CD4 ≥ 300 cells/mm³ at pre-entry visit within 14 days prior to enrollment.
7. Ability to sign informed consent and willingness to comply with the study requirements and clinic policies.
8. No evidence of viral hepatitis co-infection as assessed by Hepatitis C antibody, HCV RNA, and hepatitis B surface antigen; determinations at pre-entry visit within 28 days prior to enrollment.
9. No history of or evidence of autoimmune hepatitis or other autoimmune disorders at screening, or antinuclear antibody (ANA $> 3x$ upper limit of normal).
10. Laboratory values at pre-entry visit within 14 days prior to enrollment:
 - Alkaline phosphatase < 2.0 times upper limit of normal
 - Alanine transaminase (ALT) < 2.0 times upper limit of normal
 - Total bilirubin < 2.5 mg/dL (< 40 mg/dL if on Atazanavir)
 - Creatinine clearance ≥ 60 mL/min as estimated by the Cockcroft-Gault equation
 - Neutrophil count ≥ 1500 cells/mm³
 - Platelets $\geq 150,000$ / mm³
 - Hemoglobin ≥ 12.0 mg/dL for men and > 11.0 g/dL for women
 - Fasting glucose < 126 mg/dL
11. No history or evidence of significant clinical depression at screening that in the opinion of the investigator would affect the ability of the patient to participate in the study, or which would constitute a threat for his/her health in case of relapse upon INF treatment. The Beck Depression Inventory score must be ≤ 13 at pre-entry visit.
12. No history of INF/PEG-INF therapy.
13. If capable of pregnancy: use of effective contraception during study: effective contraception methods include abstinence, surgical sterilization of either partner, barrier methods such as diaphragm, condom, cap or sponge, or use of hormonal contraception with an anti-HIV regimen that will not alter metabolism of hormonal contraception.

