12.1 Study Drugs and Procedures

12.1.1 Pegylated Interferon Alpha 2b

Interferon alpha is a cytokine with proven antiviral activity against many viruses, especially HCV. The exact mechanism of this antiviral activity is not known. The proposed mechanisms of actions for interferon alpha are:

1. Antiviral activity through the inhibition of viral replication in infected cells (Sen 2001, Bekisz, Schmeisser et al. 2004, Jiang, Guo et al. 2008). With respect to HIV-1 specifically, INF has shown antiviral activity both *in vitro* (Ho, Hartshorn et al. 1985) and *in vivo* (Lane, Kovacs et al. 1988, Hatzakis, Gargalianos et al. 2001) studies.
2. Immune regulatory actions increasing the ability of reticuloendothelial cells to clear virus through the following mechanisms (Missale, Bertoni et al. 1996, Gerlach, Diepolder et al. 1999, Patel and McHutchison 2001):
 - a. Increase in class 1 MHC antigens and cellular adhesion molecules on effector cells
 - b. Activation of effector cells (NK cell and macrophages)
 - c. Upregulation of Th1-T helper subset

In participants with cirrhosis, exacerbation of cirrhosis-related neutropenia and thrombocytopenia is a recognized risk associated with interferon and pegylated interferon. Participants with documented cirrhosis will be excluded from

participating in this study. The other recognized side effects associated with the use of pegylated interferon include fatigue, headaches, myalgia, fever, nausea, upper abdominal discomfort, depression, diarrhea, insomnia, reduced appetite, and dermatitis. There are also rare occurrences of autoimmune, infections, ophthalmic, and ischemic disorders associated with pegylated interferon use. Ophthalmologic complications include retinopathy, which is usually transient and completely resolves with continued treatment. Other side effects associated with subcutaneous injection include pain and inflammation at the site of injection.

The specific adverse events listed below will be handled as specified. PEGINTRON will be administered in clinic by trained personnel. Merck Inc. will be providing study drug PEGINTRON; other study agents will be provided through respective pharmacies as indicated.

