At each contact with the subject, information regarding adverse events will be elicited by appropriate questioning and examinations. All events, both expected/unexpected and related/unrelated will be recorded on a source document. Source documents will include: progress notes, laboratory reports, consult notes, phone call summaries, survey tools and data collection tools. Source documents will be reviewed in a timely manner by the research team. All reportable adverse events that are identified will be recorded in CRIMSON, or the appropriate case report form (CRF), or source document. The start date, the stop date, the severity of each reportable event, and the PI's judgment of the AEs relationship and expectedness to the study agent/intervention will also be recorded in CRIMSON, or on the appropriate CRF, or source document.

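### The Beck score bands in Section 8.2 assign no action to a score of exactly 29, although 28 requires a psychiatric evaluation and 30 a permanent stop

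*Combined protocol and SAP*

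**What the plan says.** Three provisions set the Beck thresholds.

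- Entry (Section 4.1, item 11): "The Beck Depression Inventory score must be ≤ 13 at pre-entry visit".
- Lower and middle action bands (Section 8.2, depression row): "If a BDS score of 14-19 is reported, assessment by the site investigator will be scheduled before the next dose of study drug", and "If a BDS score of 20-28 is reported, a psychiatric evaluation is required before the next dose of study drug".
- Top band (same row): "If a BDS score is >29 or suicidal ideation is reported, participants will permanently discontinue study drug". The sentence goes on to require prompt psychiatric evaluation.

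Appendix 1 schedules the inventory at Pre-Entry 1, Entry, Visits 1 to 10 and the Final Visit. It is therefore repeated at each of the on-treatment dosing visits on Days 7, 14 and 21 (Visits 1 to 3). Section 12.1.1 gives the reason for this monitoring: "The other recognized side effects associated with the use of pegylated interferon include fatigue, headaches, myalgia, fever, nausea, upper abdominal discomfort, depression" and others.

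**The concern.** A graded safety rule should ask for at least as much at a worse score as at a better one. Here the required action rises from 14 to 28, disappears at 29, and reappears at its strictest at 30. The missing value is not in the middle of a band. It lies between the score that calls for a psychiatrist and the score that ends treatment.

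The Beck score is the plan's scheduled measure of a recognized effect of the study drug, and Section 14 describes the trial as offering participants no benefit. At stake is whether a participant with a high depression score is certain to be evaluated before another dose, or whether that depends on the judgement of the clinician on the day.

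**Working it through.** No sample size, power or alpha is involved. The check is whether the bands cover every score, and then whether another provision fills any hole.

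**Step 1. Inputs.** The entry limit is 13 or less (Section 4.1). The action bands are 14-19, 20-28 and >29 (Section 8.2). Scores are taken as whole numbers, which the cut-points imply.

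**Step 2. Coverage as written.** Each score *s* from 14 upward is tested against 14 ≤ *s* ≤ 19, 20 ≤ *s* ≤ 28 and *s* > 29.

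| Score | Action required by the score |
|---|---|
| 13 or less | none needed (meets the entry limit) |
| 14 to 19 | investigator assessment before next dose |
| 20 to 28 | psychiatric evaluation before next dose |
| 29 | none |
| 30 or more | permanent stop and prompt psychiatric evaluation |

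No score falls in two bands. The only score from 14 upward that falls in none is 29.

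**Step 3. Coverage after the change.** With the third condition as *s* ≥ 29, every score from 14 upward falls in exactly one band. Extending the middle band to 20-29 and leaving >29 alone gives the same complete coverage.

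**Step 4. Does another provision act on a 29?**

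- *Section 7.3* lets adverse events of Grade 2 or lower continue at the current dose and permits extra visits. It ties no Beck score to a grade and requires no evaluation.
- *Section 8.1* applies to life-threatening or Grade 4 events related to treatment, not to a score.
- *Section 8.3 item 3* ends study drug for clinical depression. It gives no score and does not itself require the evaluation that would establish the diagnosis.
- *Section 8.3 items 7 and 8* rest on investigator judgement.
- *Section 9.1* says "results of safety tests will be reviewed by the site investigator at each visit before PEG-Interferon administration", but it sits under serum chemistry and hematology and concerns laboratory tests.
- *Section 15, Recording/Documentation* makes it likely that a 29 would be seen: "At each contact with the subject, information regarding adverse events will be elicited by appropriate questioning and examinations", and "Source documents will be reviewed in a timely manner by the research team". It prescribes no action on dosing.
- *Appendix 1* has a psychiatric evaluation row marked only at Pre-Entry 1 and Entry. The condition attached to those marks cannot be read in the available text, so this row may or may not apply to a 29 at Entry. It has no mark at Visits 1 to 3.

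None of these provisions is triggered by a score of 29 at the on-treatment visits.

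**The case against.** The best case for the plan is that this is a drafting slip that no sensible investigator would exploit. With an evaluation required at 28 and a stop at 30, nobody would read 29 as needing nothing. Suicidal ideation stops drug at any score, and so does clinical depression under Section 8.3. Questioning about adverse events continues at every contact. Most of this stands, and it is why the point is minor. It does not remove the gap, because none of those safeguards is set off by the score.

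A reader might infer that the plan allows a participant scoring 29 to be re-dosed with nothing required. The documents do not support that. Section 8.2 is silent on 29, and silence in one row does not override the clinical depression and suicidal ideation rules. A reader might also infer that nothing covers a 29 at Entry. The unreadable condition on the Appendix 1 row means this cannot be asserted.

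It could be said that the symbol lost its bar when the text was read from PDF. That cannot be excluded, but the CD4 row just above prints ≥14% intact, which makes it unlikely.

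Finally, the documents do not show which neighbouring action was intended for 29. That is fair, and it bears on the choice of fix rather than on whether one is needed.

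**Conclusion.** The point holds as a minor fault in a safety rule: Section 8.2 assigns no score-based action to a Beck score of exactly 29 without suicidal ideation. It clearly applies at Visits 1 to 3.

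Its size is one whole-number value. The documents give no basis for the chance that any of about 10 participants would score exactly 29, so no probability is offered. The consequence is confined to participant safety; no endpoint, analysis or sample size figure changes.

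The conclusion rests on two assumptions: that the inventory is scored in whole numbers, and that the printed symbol is the one in the protocol.

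**What to change.** In the depression row of Section 8.2, change >29 to ≥29. This closes the gap without overlap and is the cautious choice, since it places 29 with the stopping action. If the investigators intended evaluation rather than a stop at that score, widening the middle band to 20-29 would also close it. Either way, the protocol should say which.

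The cost of the preferred change is one character and no added visits or instruments. Its only real downside is that a participant scoring exactly 29 permanently stops study drug.

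As an editorial correction in the same amendment, Section 8.3 item 3 points to a Section 8.5, but Section 8 ends at 8.3. The reference should be to Section 8.2, where the depression row stands.
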